## **6.6 Dose Modification**

Through protocol amendment, planned doses may be decreased on an individual or group basis according to emerging safety and tolerability data.

## **6.7 Treatment After the End of the Study**

Not applicable. No subsequent open-label extension is planned following the study. Study treatment will not be available after the end of study participation.

# **7 Discontinuation of Study Treatment and Participant Discontinuation**

Refer to the SoA for data that are to be collected at the time of study discontinuation, during follow-up, and for any further evaluations that need to be completed.

## **7.1 Discontinuation of Study Treatment**

If a clinically significant finding is identified, the Investigator will determine if the participant can continue in the study and if any change in participant management is needed. Any new clinically relevant finding should be reported as an adverse event (AE).

## **7.2 Stopping Criteria**

### **7.2.1 Individual Participant Stopping Criteria**

- Incidents of abuse, diversion, or misuse of the study treatment.

- Incidents of clinical significance: hallucinations, amnesia, delusional thinking, delirium, manic symptoms, aggressive behavior, suicidality, homicidality, agitation, confusion, or convulsions/seizures.
- Participants reporting any SAE.
- Acute urinary obstruction.
- Any other AE that in the judgment of the Investigator necessitates the participant stopping to protect participant safety.

Participants discontinued from dosing will undergo end of study procedures with follow-up monitoring of the AE(s) as clinically indicated.

### **7.3 Participant Discontinuation/Withdrawal from the Study**

- A participant may withdraw from the study at any time at his/her own request or may be withdrawn at any time at the discretion of the Investigator for safety, behavioral, or administrative reasons.
- If the participant withdraws consent for disclosure of future information, the Sponsor may retain and continue to use any data collected before such a withdrawal of consent.
- All participants who withdraw from the study with an ongoing AE must be followed until the event is resolved or deemed stable.
- Participation may be terminated before completing the study and the reason recorded as follows:
  - Withdrawal due to AE
  - Withdrawal due to incident abuse, diversion, or misuse of the study treatment
  - Loss to follow-up
  - Participant withdrew consent at own request
  - Other

## 7.4 Loss of Participants to Follow-Up

A participant will be considered lost to follow-up if he or she repeatedly fails to return for scheduled visits and is unable to be contacted by the study site. The following actions must be taken if a participant fails to return to the clinic for a required study visit:

- Study staff must attempt to contact the participant and reschedule the missed visit as soon as possible (and within the visit window, where one is defined) and counsel the participant on the importance of maintaining the assigned visit schedule and ascertain whether or not the participant wishes to and/or should continue in the study.
- In cases in which the participant is deemed lost to follow-up, the Investigator or designee must make every effort to regain contact with the participant (where possible, 3 telephone calls and, if necessary, a certified letter to the participant's last known mailing address or local equivalent methods). These contact attempts should be documented in the participant's medical record/eCRF.
- Should the participant continue to be unreachable, he/she will be considered to have withdrawn from the study.

## 8 Study Assessments and Procedures

- Study procedures and their timing are summarized in the SoA.
- Adherence to the study design requirements, including those specified in the SoA, is essential and required for study conduct.
- All screening evaluations must be completed and reviewed to confirm that potential participants meet all eligibility criteria. The Investigator will maintain a screening log to record details of all participants screened and to confirm eligibility or record reasons for screening failure, as applicable.

### 8.1 Efficacy Assessments

#### 8.1.1 Efficacy Endpoint Scales

- The OSA-18 is an 18-question pediatric OSA-specific health-related quality of life questionnaire. The ESS is a self-administered questionnaire with 8 questions. Respondents are asked to rate, on a 7-point scale (1-7) how frequently they experience OSA-related symptoms or problems. The OSA-18 score is a sum of 18 item scores (range 18-126), with higher scores indicating lower quality of life. The questionnaire takes approximately 5 minutes to answer. The OSA-18 is a secondary outcome and is measured at all PSG visits.

- The Peds-QL is a 23-question general pediatric health-related quality of life questionnaire with subscales for physical, emotional, social and school function. Respondents rate common problems on a scale from 0-4. Answers are reverse-scored and linearly transformed to a 0-100 scale, with lower scores indicating worse quality of life. The questionnaire takes approximately 5 minutes to answer. The Peds-QL is an exploratory outcome and is measured at all PSG visits. A change of 4.36 in Peds-QL total scale score has been shown to represent the minimal clinically important significant difference.
- The Caregiver Global Impression of Change scale consists of a 1-item questionnaire designed to assess the caregiver's satisfaction with the experimental treatment, considering both safety and efficacy. The scale is administered at the end of both high dose ato-oxy and low dose ato-oxy treatment periods.
- The Vineland 3 is a validated measure of adaptive behavior commonly used in studies of children with developmental disabilities such as Down syndrome. This is an exploratory outcome and is measured at all PSG visits. The adaptive behavior composite scale will be the outcome of interest.
- The Conners 3rd edition is a validated measure of behavior, primarily related to attention. This is an exploratory outcome and is measured at all PSG visits. The Conners ADHD Index will be the outcome of interest.

### 8.1.2 Polysomnography

- Methods: Standard overnight PSG recording and data interpretation will be performed in accordance with the American Academy of Sleep Medicine (AASM) scoring manual. Participants will be instrumented with standard PSG electrodes. Time of lights out will be established according to the participants' habitual schedule and kept constant across the PSG study nights. The participants will be given approximately 8 hours of time in bed.
- Technically Adequate Test: The screening/baseline PSG study must meet the following criteria for participants to enroll:
  - At least 4 hours of sleep.
  - At least 2 electroencephalograms (EEGs) and 2 electrooculography traces for the full night.
  - P nasal for at least 60% of the night and thermistor or both respiratory belts signals for the full night for scoring respiratory events.

Participants who do not have a technically adequate test at baseline can be retested at the discretion of the investigator.

- Scoring: Scoring will be conducted according to the American Academy of Sleep Medicine manual scoring criteria. All studies will be reviewed and overscored by a board-certified pediatric sleep medicine specialist blinded to study randomization.

## 8.2 LENA Language Evaluation

Language evaluation will be done using the Language ENvironment Analysis (LENA) digital language processor (LENA Foundation, Boulder, CO). The LENA device has been used in studies in children with developmental disabilities for more than 10 years, with 16 publications including children with developmental disabilities listed on the LENA device website bibliography (<https://www.lenafoundation.org/wp-content/uploads/pdf/ResearchPublications.pdf>). Additionally, it is included in ongoing NIH-funded studies in children with developmental disabilities, including the current PANDABox study (grant # MH111955).

The LENA device has been previously used in children with Down syndrome and has shown that sleep problems were associated with worse language abilities in children with Down syndrome(Edgin, Tooley et al. 2015). Similarly, in a prior study of OSA in children with Down syndrome, verbal IQ was specifically impaired(Breslin, Spano et al. 2014). Given these prior findings, it follows that OSA treatment may lead to improvement of language abilities in children with DS. There are no published studies to our knowledge evaluating the effects of OSA treatment on language in children with DS. This may be potentially in part due to the associated difficulties of performing laboratory-based assessments of language in children with Down syndrome, which may be a lengthy and stressful experience for the child. The LENA device provides a low-stress language evaluation that takes place in the child's own home. This provides a snap-shot of the child's language abilities in their natural environment.

LENA is a wearable digital recorder that stores 16 continuous hours of the sound environment for later analysis by LENA software speech-identification algorithms or manual coding. Children will wear the device on a necklace for a full day of recording at baseline as well as in the last week of each ato-oxy dose regimen. LENA software will be used to extract language-related variables (including total vocalizations of the child, total number of conversational turns of the child as well as measures of language complexity such as longest utterance of the child). Following download and extraction of these variables, the raw audio recording from the LENA device will be destroyed. This means that no human review of the audio recording will be performed, eliminating the risk of any inadvertent disclosure of private information from either consented individuals or background individuals. Additionally, consent for the LENA portion of the study will be “opt-in,” and parents will initial a separate box to indicated interest in participating in this optional portion of the study. Participants will also be reminded prior to each

LENA recording that this is an optional procedure. They will also be provided with instructions on how to pause the device, as well as told that they can request to have the recording deleted without analysis if desired after completion of the procedure.

The primary goal of inclusion of the LENA device will be to determine feasibility of including this outcome in future studies. Specifically, our outcome will be the percentage of participants with usable data at all three study timepoints.

### **8.3 Safety Assessments**

- Planned time points for all safety assessments are provided in the SoA.
- Safety monitoring will be guided by the established safety profiles of atomoxetine and oxybutynin, and by Phase 1 safety data for the combination. Safety assessments will include measurement of vital signs, monitoring and recording of AEs, SAEs, suicidality assessment, recording of study or treatment discontinuations. Effects on OSA and sleep parameters (e.g., sleep time and sleep stages) will also be monitored by PSG.
- Adverse events of special interest include effects on urine outflow, as both atomoxetine and oxybutynin are associated with urinary retention. Effects of atomoxetine on heart rate and blood pressure are expected to be modest, as indicated by the initial data described above, and will also be monitored. Participants with congenital heart disease will require clearance from their cardiologist in order to participate in the study. Suicidal ideation in children and adolescents is a boxed warning for atomoxetine. Therefore, safety monitoring in the dose-finding study will use an appropriate questionnaire to monitor for the potential emergence of suicidal ideation or depression. We will also specifically monitor for symptoms of reactive airway disease during safety monitoring. This will include questions related to wheezing as well as use of bronchodilator medications.

#### **8.3.1 Vital Signs**

- Assessment of vital signs (seated blood pressure, pulse rate,) will be performed at the time points indicated in the SoA (Section 1.3).
- Vital signs will be measured at all visits in a seated position after 5 minutes rest and will include systolic/diastolic blood pressure and pulse. Measurements should be made in the same arm of the participant at each visit.
- Systolic and diastolic blood pressure will be repeated for a total of 3 measurements, each at least 2 minutes apart.

### 8.3.2 Clinical Safety Laboratory Assessments

- To minimize discomfort to the child participants of the study, no routine blood draws will be included as part of the study. Both study agents are FDA-approved and do not require any laboratory monitoring.
- A urine pregnancy test will be performed on all female participants age 10 and older prior to study randomization.
- There are case reports of liver toxicity associated with atomoxetine, however large scale studies have not shown any increased risk of liver toxicity. There were no cases of liver-related SAEs during all clinical trials of atomoxetine in children and adults, which included 7,691 participants. Additionally, there are only three reports of liver toxicity related to atomoxetine in post-marketing surveillance of atomoxetine (with >10 years of monitoring), which all resolved with drug discontinuation. Therefore, to minimize risk of harm to participants, we will specifically inquire about evidence of jaundice or skin color changes during weekly phone calls while on study drugs but will not require blood draws for all participants. Participants that are found to have jaundice will have study drug discontinued and be referred for further medical management. These participants will be monitored until their condition stabilizes or resolves.

### 8.3.3 Suicide Risk Monitoring

Suicidal ideation in children and adolescents is a boxed warning for atomoxetine. However, post-marketing safety data has not shown an increased risk of suicidality associated with atomoxetine use (Bangs, Wietecha et al. 2014, Reed, Buitelaar et al. 2016). Additionally, suicidality appears uncommon in individuals with DS, regardless of atomoxetine use. There are no reports of suicide or suicidal ideation occurring in any children or adolescents with Down syndrome (DS), and a total of three reported suicide attempts in older individuals with DS (none associated with atomoxetine). Given this, the likelihood of suicidal ideation appears very low for this study. To further reduce the risk of suicide, we have excluded participants with current depression. Given the paucity of literature on suicidal ideation in DS, there are no available screening tools available for suicidality in DS. Therefore, we will instead monitor mood using the depression subscale of the Anxiety, Depression and Mood Scale (ADAMS), a screening tool for individuals with cognitive impairment which has been validated in a sample that included children with DS. In addition, we will use a single screening question from the Child Behavior Checklist (a validated behavior questionnaire for age 6-18) for suicidality: “Does your child talk about killing themselves?” For subjects that answer positively (somewhat true or often true), they will be flagged for immediate detailed assessment by the study PI, and appropriate actions will be taken,

including discontinuation of study medication as well as referral to behavioral health emergency services if indicated. This screening will occur weekly while subjects are on study medications. If this occurs, participants would be monitored until their suicidal ideation resolves.

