**Treatment Groups and Duration:**

All participants will receive both high dose ato-oxy and low dose ato-oxy in random order.

[figure not shown]
The overall study duration will be up to 15 weeks, as follows:

- Up to 28 days for screening and baseline PSG;
- 28 nights of high dose ato-oxy (with PSG and health-related quality of life assessment on the last night of high dose ato-oxy)

- 14-21 days of wash-out period between high dose ato-oxy and low dose ato-oxy periods
- 28 nights of low dose ato-oxy (with PSG and health-related quality of life assessment on the last night of low dose ato-oxy)

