## 4 Study Design

### 4.1 Overall Design

This is a randomized, double blind, cross-over study of the combination of atomoxetine and oxybutynin in children with DS and OSA documented by polysomnography (PSG).

Approximately 27 participants will be randomized in the study. Participants will receive high dose ato-oxy for four weeks as well as low dose ato-oxy for four weeks in random order. During the high dose ato-oxy period, participants will take 5 mg oxybutynin and 0.5 mg/kg/day (max 40 mg) atomoxetine nightly for one week. Atomoxetine dose will then be increased to 1.2 mg/kg/day (max 80 mg) and oxybutynin will remain at 5 mg. During the low dose ato-oxy period, participants will take 5 mg oxybutynin and 0.5 mg/kg/day (max 40 mg) atomoxetine nightly. Overall study duration will be 10-15 weeks. Dosing of the study treatment will occur approximately 30 minutes prior to bedtime. Participants who withdraw from the study will not be replaced.

Study participants will undergo eligibility screening that will include an initial screening to determine whether non- PSG enrollment criteria are met, followed by a 1 night in-lab PSG and health-related quality of life assessment for participants who qualify based on non-PSG criteria. For participants who are eligible and enroll in the study, the screening PSG night will serve as the baseline measure for apnea hypopnea index (AHI) and other PSG endpoints. On the final night of dosing for both high dose ato-oxy and low dose ato-oxy, participants will return for inpatient PSG and health-related quality of life assessment. The primary efficacy endpoint is the change in obstructive AHI from baseline (high dose ato-oxy vs. low dose ato-oxy).

**Figure 2:** Overview of Study Design

Participants will be randomized to either high dose ato-oxy or low dose ato-oxy at baseline. Polysomnography (PSG) and health-related quality of life (HR-QOL) assessment will be performed after four weeks of treatment. Participants will then take no drug for two weeks, then take the alternate treatment for four weeks with repeat PSG and HR-QOL assessment at the end of therapy.

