## 5 Study Population

The study population will consist of male and female participants between 6 and 17 years of age, inclusive, with a documented history of DS and OSA on initial study PSG. Participant's parent or guardian must be able to provide written consent and meet all the inclusion criteria and none of the exclusion criteria.

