### 5.2 Exclusion Criteria

Participants are excluded from the study if any of the following criteria apply:

Exclusion Criteria at study entry (prior to baseline polysomnography)
1. Presence of central sleep apnea on polysomnography (central AHI $\geq 5$ )

2. Currently using and adherent to PAP therapy (>4 hours per night for 70% of nights in the past 30 days based on device download or parent report)

3. MAO inhibitor use

4. Urinary retention

5. Prematurity < 37 weeks estimated gestational age

6. Seizure disorder

7. Untreated or inadequately treated hypothyroidism

8. Significant traumatic brain injury

9. Congenital heart disease and not cleared to participate by the patient's cardiologist

10. History of current, untreated depression

11. History of liver disease

12. 3+ or greater tonsillar hypertrophy

13. Positive urine pregnancy test

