## **6.5 Concomitant Therapy**

Concomitant therapy with the following medications is disallowed:

- MAOIs or other drugs that affect monoamine concentrations (e.g., rasagiline) [MAOIs are contraindicated for use with atomoxetine]
- CYP2D6 inhibitors
- Strong CYP3A4 inhibitors (e.g., ketoconazole)
- Benzodiazepines and other anxiolytics

- Opioids
- Sedatives including nonbenzodiazepine “Z-drugs” (zolpidem, zaleplon, eszopiclone)
- Muscle relaxants
- Pressor agents
- Drugs with clinically significant cardiac QT-interval prolonging effects
- Drugs known to lower seizure threshold (e.g., chloroquine)
- Antiepileptics
- Antiemetics
- Modafinil or armodafinil
- Anticholinergics and anticholinesterase inhibitors, including drugs with substantial anticholinergic side effects, (e.g., first generation antihistamines)
- Sedating antihistamines
- Pseudoephedrine, phenylephrine, oxymetazoline

Medications that do not have substantial effects on the central nervous system (CNS), respiration, or muscle activity are generally allowed if dose and frequency is stable for 3 months prior to enrollment and during the course of the study, including, but not necessarily limited to, the following drugs and drug classes:

- Antihypertensives (angiotensin-converting-enzyme/angiotensin II receptor blocker inhibitors, calcium channel blockers, spironolactone, hydrochlorothiazide, etc.)
- Statins
- Proton pump inhibitors and histamine h2 receptor blockers
- Over-the-counter (OTC) antacids
- Non-sedating antihistamines (e.g., cetirizine, loratadine)
- Melatonin
- Non-steroidal anti-inflammatory drugs and acetaminophen
- Laxatives
- Inhaled corticosteroids (e.g., fluticasone)

- Antidiabetics
- Ocular hypotensives and other ophthalmics (e.g., timolol)
- Hormonal therapy (e.g., estrogen replacement or anti-estrogens) and hormonal contraceptives
- Thyroid medications
- Anticoagulants
- OTC topicals (e.g., topical pain relievers)
- Patients currently on medications for Attention Deficit Hyperactivity Disorder will be included, but should not change their medication regimen/dosage during the study.

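### Section 8.3.3 says children with current depression are excluded, but exclusion 10 removes only those whose current depression is untreated

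*Combined protocol and SAP*

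**What the plan says.** Section 8.3.3 (Suicide Risk Monitoring) notes the boxed warning, argues that suicidality is rare in Down syndrome, judges the likelihood in this study very low, and then lists what is done to lower it further. The first measure is that "we have excluded participants with current depression". The sentence makes no distinction by treatment status.

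Section 5.2 (Exclusion Criteria), item 10 of the study-entry list, reads "History of current, untreated depression". Section 5 makes the lists decisive: a participant must "meet all the inclusion criteria and none of the exclusion criteria".

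Three other provisions bear on the point:

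- Section 6.5 disallows "MAOIs or other drugs that affect monoamine concentrations", CYP2D6 inhibitors and drugs with clinically significant QT prolongation, among others. It names neither antidepressants nor depression.
- Section 8.3.3 adds the ADAMS depression subscale and one Child Behavior Checklist question on suicidality. On timing it says: "This screening will occur weekly while subjects are on study medications".
- Section 7.2.1 makes suicidality a reason to stop dosing, in a list that includes "aggressive behavior, suicidality, homicidality, agitation, confusion, or convulsions/seizures".

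**The concern.** The two statements describe different populations. Section 8.3.3 tells an ethics board or data monitoring board that no child with current depression will receive the drug. Section 5.2, which sites apply, turns away only those whose depression is untreated. A site that follows the protocol to the letter can enrol a child whom the safety section says is not in the trial.

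This matters because the safeguard acts before the first dose, on a risk that carries a boxed warning in this age group. The remaining safeguards detect trouble during treatment; they do not decide who is exposed. Exclusion 10 is the only eligibility criterion that deals with depression.

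**Working it through.** The plan states no figure on this point, so the main check is a comparison of texts. A little arithmetic then describes the planned exposure.

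**1. The two definitions**

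| Place | Group kept out |
|---|---|
| 8.3.3 | All current depression |
| 5.2, item 10 | Current depression that is also untreated |

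The second group is a strict subset of the first. The difference is current depression under treatment.

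**2. Could another eligibility rule cover the difference?** The inclusion criteria in 5.1 concern age, Down syndrome diagnosis, and consent or assent. The exclusions applied after baseline polysomnography concern hypoxaemia, central apnoea and absence of OSA. None mentions depression.

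**3. Could item 10 be read more widely?** Its wording is awkward, since it asks for a history of something current, but no natural reading brings in treated cases. Item 7 of the same list, on hypothyroidism, covers both the untreated and the inadequately treated. Item 10 has no such second limb, so even depression that is treated but poorly controlled does not meet it.

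**4. Does section 6.5 close the gap?** In part.

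- *Drug treatment.* The bars on monoamine-affecting drugs, CYP2D6 inhibitors and QT-prolonging drugs may rule out some children on antidepressants. The section also generally allows only medicines without substantial central nervous system effects, which narrows the gap further. But it does not spell out how this applies to antidepressants, and the monoamine bar cannot be read as absolute: 6.5 admits children on ADHD medication, and section 2.2.3 describes atomoxetine, itself an ADHD drug, as a norepinephrine reuptake inhibitor.
- *Treatment without drugs.* A concomitant-medication list cannot reach a child treated by psychotherapy alone.

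**5. Do the monitoring rules replace the exclusion?** The weekly screening is set for the time on study drug. The Schedule of Activities shows no depression measure at Visit 1; the behavioural instruments listed there are the Conners-3 and the Vineland 3. The stopping rule in 7.2.1 takes effect only after an event.

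**6. Planned exposure of a child who enters this way**

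Inputs: 28 nights in each period (section 1.1), all participants receiving both doses, the first week of the high-dose period at 0.5 mg/kg (section 4.1), and 27 randomised (section 1.1).

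- Atomoxetine nights: 28 + 28 = 56.
- Nights at 1.2 mg/kg (max 80 mg): 28 − 7 = 21, approximate because visits may move by up to 4 days.
- One child as a share of those randomised: 1/27 = 3.7%.

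These figures describe any participant's planned exposure. They do not estimate risk or the chance that such a child enrols.

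**The case against.** The strongest reply is that this is loose paraphrase with little practical effect. Exclusion 10 carries a deliberate qualifier, and the sentence in 8.3.3 is a one-line summary in a rationale paragraph, so the summary may be what is wrong. Section 6.5 bars many drug classes and generally allows only medicines without substantial central nervous system effects. No listed allowed class is an antidepressant, so few drug-treated children may get through. The protocol considers suicidal ideation very unlikely in this population. Weekly screening with immediate assessment, the stopping rule and the investigator's discretion to withdraw a child for safety (7.3) all remain.

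Much of this stands:

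- The clearly demonstrated gap is depression managed without drugs. For drug-treated children the gap depends on how a site reads 6.5.
- The number affected is unknown and may be zero.
- The documents do not show which text reflects the sponsor's intent.

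None of it reconciles the two statements. If 8.3.3 is the loose text, the protocol is claiming a protection it does not have, on a boxed-warning risk. If 5.2 is the loose text, the entry rule admits children it was meant to exclude. One of them has to change.

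**Conclusion.** The inconsistency is real. The exclusion described in 8.3.3 is only partly in force, because exclusion 10 leaves out current, treated depression and nothing else in the eligibility criteria covers it. Section 6.5 narrows the gap without closing it, and the monitoring rules act only after exposure starts.

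The consequence concerns participant safety and the accuracy of what oversight bodies are told. The primary endpoint, its analysis and the power are untouched. The size cannot be stated as a number of children, because the documents give no prevalence of treated depression in this population.

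The conclusion rests on two readings: that section 5.2 governs entry, as section 5 says, and that *untreated* in item 10 has its ordinary meaning.

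**What to change.** Decide which population is intended and make the two sections agree.

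- **If all current depression is to be excluded** (what 8.3.3 tells readers): reword exclusion 10 as *Current depression (treated or untreated)* and carry the wording into the screening checklist. A few children with treated depression become ineligible, in a trial of about 27.
- **If treated children are to be enrolled:** change 8.3.3 to say that only current, untreated depression is excluded, and add a sentence justifying the enrolment of treated cases. Eligibility does not change.

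I would take the first option, because it delivers the safeguard the protocol already claims. The drafting is a few words either way. The first option changes eligibility, so it needs an amendment with IRB approval before use (sections 10.1.1 and 10.1.12). The second corrects a safety statement and should also go to the IRB. Neither affects the sample size or the analysis.

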- 6 Vital signs include the following: seated blood pressure, pulse, Participants who experience systolic blood pressure  $\geq 140$ , or diastolic blood pressure  $\geq 90$ , or heart rate  $\geq 130$  beats per minute will be further evaluated.
- 7 Quality of life assessment will include completion of the OSA-18, Peds-QL and caregiver global impression of change. Behavioral assessments will include the Conners-3 and Vineland 3rd edition.
- 8 Daily bedtime dosing continues through the next PSG visit (for 28 days of therapy). The final night of study treatment dosing is PSG night.
- 9 Language assessment using the LENA device may take place at any point in the baseline period prior to drug administration (preferably within the week preceding baseline polysomnography, and will be repeated at any point within the last week of each drug regimen (prior to polysomnography)

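### No pre-dose ADAMS depression or suicidality reading is specified, and the Schedule of Activities names neither instrument, so a positive finding at the first on-drug contact has no off-drug reference

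*Combined protocol and SAP*

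**What the plan says.** Section 8.3 counts suicidality among the safety assessments ("monitoring and recording of AEs, SAEs, suicidality assessment, recording of study or treatment discontinuations") and states where their timing is to be found: "Planned time points for all safety assessments are provided in the SoA". It gives the aim as using an "appropriate questionnaire to monitor for the potential emergence of suicidal ideation or depression".

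Section 8.3.3 names two tools. For mood, "we will instead monitor mood using the depression subscale of the Anxiety, Depression and Mood Scale (ADAMS". For suicidality, "we will use a single screening question from the Child Behavior Checklist". A positive answer to that question leads to immediate assessment by the study's principal investigator. The only timing is: "This screening will occur weekly while subjects are on study medications".

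Table 1 (Section 1.3) has no row for either tool. Footnote 7 lists the OSA-18, Peds-QL and caregiver global impression under quality of life, and adds that "Behavioral assessments will include the Conners-3 and Vineland" 3rd edition. The adverse event screening row is marked at Phone Calls 1-6 and Visits 2 and 3. It is not marked at Visit 1 or in either dispensing column (Day 1 and Day 42).

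On entry, exclusion 10 in Section 5.2 covers depression that is both current and untreated. Section 8.3.3 describes the same exclusion as covering current depression, without the untreated qualifier. No criterion mentions suicidal ideation.

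**The concern.** To show that something emerged on treatment, the plan needs to know the state before treatment. Every specified reading is taken on study medication, and both regimens contain atomoxetine, so the plan as written has no off-drug value on either instrument. A child with an existing low mood, or whose caregiver would already answer the question positively, would first be identified on drug.

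Three other parts of the protocol depend on that distinction:

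- Section 10.2 counts a condition first detected after dosing as an adverse event even if it was present earlier, but leaves out ordinary fluctuation of conditions detected at the start. Whether a reading was taken at the start can therefore change the classification.
- Section 10.2 also requires a causality judgement for every event.
- Suicidality is an individual stopping criterion in Section 7.2.1, and Section 4.1 says withdrawn participants are not replaced, in a trial of about 27.

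There is also a practical risk. Section 8 makes adherence to the SoA essential, and a site working from Table 1 would find neither tool named there.

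**Working it through.** The plan gives no figure on this point to reproduce. The check sets the sections against each other, counts contacts, and asks which result patterns can be read.

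**1. Timing.** Section 8.3 sends the reader to the SoA for all safety time points. Table 1 and its nine footnotes name neither instrument. Section 8.3.3 alone gives timing, and only on drug. No section specifies a pre-dose or washout reading, and none forbids one.

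**2. Contacts.** Assumption: the weekly screening uses the adverse event screening contacts, the only weekly on-drug contacts in Table 1.
- Marked days: 7, 14, 21, 28, 49, 56, 63, 70 = 8 of 11 columns, all on drug.
- Over 27 children: 27 × 8 = 216 scheduled on-drug readings.
- Readings before the first dose, or between washout and the second regimen: 0.

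**3. Exposure before the first reading.** Phone Call 1 is Day 7±4, so Days 3 to 11. With nightly dosing from Day 1 and a daytime call, prior doses = call day − 1.
- Day 3: 2 doses. Day 7 (nominal): 6 doses. Day 11: 10 doses.
- In the high dose period the step-up follows one week, so it starts on night 8. At the nominal call all 6 doses are at the starting level. Only late calls follow the step: by Day 11, nights 8, 9 and 10 = 3 doses at the higher level.

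**4. Which patterns can be read.**
- Negative at Call 1, positive later: new since Call 1. Readable.
- ADAMS score at the end of the high dose period against the end of the low dose period, same child: a dose contrast. Readable.
- First positive, or already raised, at Call 1: either present before drug or early onset. Not separable on the instruments.
- Shift in ADAMS score from off drug to on drug: not observed in either period, since both start at 0.5 mg/kg atomoxetine.

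**5. Pre-dose screening.** Exclusion 10 does apply before dosing. It names no tool and no suicidality question. As worded in Section 5.2, a child with treated depression may enter; as described in Section 8.3.3, a child with current depression may not. The two passages must be reconciled.

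**6. Illustration.** The documents give no rate of positive answers at baseline and call suicidal ideation very unlikely. For an assumed share p already positive, the chance of at least one such child among 27 is 1 − (1 − p)^27:

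| Assumed p | Chance of at least 1 in 27 |
|---|---|
| 0.5% | 12.7% |
| 1% | 23.8% |
| 2% | 42.0% |
| 5% | 75.0% |

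These values show only how the chance depends on p. They are not estimates for this trial.

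**The case against.** The best defence has four parts.

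- **Depression is screened before dosing.** Exclusion 10 does this, so it would be wrong to infer that no child is screened before the first dose. This stands. What is missing is a named instrument and any question on suicidality.
- **The SoA may cover the screening without naming it.** Section 8.4.2 treats suicidality monitoring as part of adverse event detection, alongside liver toxicity and reactive airway disease, and none of these has its own row. The weekly adverse event row fits the stated frequency. A reader might infer that the SoA has no place for the screening at all; the documents do not support that. The reading is plausible and makes the on-drug part of the gap one of labelling. It does not supply a pre-dose reading, because that row begins at Phone Call 1.
- **Attribution is not lost altogether.** A reader might infer that a positive finding can never be related to drug or dose. That is too strong. Each child takes both regimens after a 14-21 day washout, a nominal Call 1 in the high dose period precedes the step-up, later new positives can be dated, and the investigator can ask about onset when a positive answer is assessed. All of this stands. It leaves the first on-drug reading unresolved on the instruments, and onset recalled after a positive answer is weaker evidence than a value recorded beforehand.
- **The event is expected to be very rare.** Section 8.3.3 says so for suicidal ideation. That lowers the expected number of ambiguous cases but does not help to interpret one, and the ADAMS subscale measures depression, not ideation alone.

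**Conclusion.** The point holds in a limited form. No pre-dose administration of either instrument is specified, the SoA names neither although Section 8.3 says it times all safety assessments, and both periods contain atomoxetine. The plan therefore has no off-drug reference for the emergence it sets out to detect. The loss is confined to positive answers or raised scores at the first on-drug contact, and to the off-drug-to-on-drug shift in mood score.

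The size is 8 scheduled on-drug readings per child and none off drug, with the first after 2 to 10 doses (6 at the nominal day). These counts assume that screening follows the adverse event contacts and that dosing starts on the night of Day 1. That no baseline is planned is inferred from the stated schedule and from silence elsewhere; a site could still take one.

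A pre-dose value would show whether a finding preceded treatment. With no placebo period, it would not by itself establish cause.

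**What to change.** Add one row to Table 1 for the ADAMS depression subscale and the Child Behavior Checklist question. Mark it at Visit 1 (completed and reviewed before randomization), before the second regimen is dispensed, and at Phone Calls 1-6 and Visits 2-3. State that on-treatment results are reported against the pre-dose value: Visit 1 as the reference before any study drug, and the later reading as the reference for the second period. Define what counts as a treatment-emergent change from those values.

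In the same edit, correct the cross-reference in Section 8.4.2, which points to 8.2.3 for suicidality monitoring when the text is in 8.3.3.

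The sponsor's clinicians should reconcile the depression exclusion in Section 5.2 with its description in Section 8.3.3, and decide how a positive baseline answer is handled. This review proposes no rule for either.

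The cost is a few minutes of caregiver time at Visit 1 and again around the second dispensing, both already in the schedule, plus one SoA row. The sample size and efficacy analyses are unaffected.
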